Participants in this trial will use RESPeRATE, a small, commercially-available guided-breathing device manufactured by Intercure, Ltd. that is currently FDA-approved for treatment of mild hypertension. The

RESPeRATE device includes a belt-type respiration sensor that is placed around the user's chest over the clothing, along with a small computerized box that generates musical tones transmitted through attached earphones. Using the belt-type sensor, the device first senses the user's spontaneous respiratory rate, while playing quiet, relaxing, non-rhythmic music. The device then begins to play distinct musical tones to guide the user in slowing her respiratory rate and prolong her expiratory phase. In the proposed clinical trial, women will be

randomized to receive either: 1) a standard, active RESPeRATE device that guides the user in breathing at a rate slower than 10 BPM, or 2) an identical-appearing control device that does not pace respiration but continues to monitor spontaneous breathing rate while playing relaxing, non-rhythmic music. Participants in both groups will be instructed to use their devices for at least 15 minutes per day for 12 weeks.

D.4.2 Active intervention

Participants who are randomized to the active intervention group will receive an active RESPeRATE device at the baseline visit that is programmed to pace respiration at less than 10 BPM (identical to current FDA-approved use of the device for treatment of hypertension). After reading the device instructions, the participant will be asked to place the belt-like elastic strap respiratory sensor around the upper chest over clothing under the axillae and above the breasts. The participant will then place the headphones on the ears and breathe normally until the device recognizes her normal respiratory rate.

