After sensing the participant's normal respiratory pattern, the active device will begin to play a distinct musical tone to prompt inspiration and a second tone to prompt expiration. The device will first synchronize its tones to the user's spontaneous respiratory pattern, and then gradually increase the timing and duration of its tones to guide the user in slowing her respiratory rate and prolonging her expiratory phase. The participant will be instructed to simply try to match her inspiration and expiration to the tones. Participants will be asked to use the RESPeRATE device for at least 15 minutes per day at home while sitting quietly and alone in a comfortable location, not listening to other music, watching television, reading, sleeping, or performing any other distracting activity.

During practice sessions, the active device will automatically collect data on: a) the time, date, and number of sessions in which it was used; b) duration of time for each practice session; c) average and range of respiratory rate; d) data quality (i.e., percent time that breathing was detected by the sensor), e) amount of time

that the participant succeeds in slowing respiration to less than 10 BPM in each session, and f) the percentage of time that the participant's breathing pattern follows the device's musical tones. Participants will be instructed to use RESPeRATE for at least 15 minutes per day for a total of 12 weeks.

D.4.3 Control intervention

Participants who are randomized to the control group will use a control RESPeRATE device that does not pace respiration, but plays relaxing, non-rhythmic music while monitoring participants' spontaneous breathing rate at home. RESPeRATE devices can be re-programmed by research staff to be either active or control devices using software provided by Intercure, Ltd., and research staff will re-program devices as needed at participants' baseline visits. The control device will look exactly like the active RESPeRATE device, except that the device will not play musical tones synchronized to inspiration and expiration, but will play quiet, non-rhythmic music while monitoring spontaneous breathing.

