Because previous studies of RESPeRATE for other indications have shown that efficacy improves with adherence,^{57,60} all women will complete a 7-day run-in period between the screening and baseline visits in which they will demonstrate willingness to adhere to home RESPeRATE practice. For the run-in, women will be given a demo RESPeRATE run-in device that plays relaxing, non-rhythmic background music but does not pace their breathing. The music played by the demo run-in RESPeRATE devices will be similar but not completely identical to the music played by the regular RESPeRATE control devices that serve as the main control intervention for the study. Like the regular RESPeRATE control device, the demo RESPeRATE control device will automatically collect data on: a) time, date, and number of sessions in which it was used; b) duration of time for each session; c) average and range of respiratory rate during each session; and d) data quality (i.e., percent time that breathing was detected by the sensor). Women will be told to use their run-in RESPeRATE devices for at least 15 minutes each day during the run-in period, while sitting quietly and alone in a comfortable location, and avoiding listening to other music, watch TV, read, sleep, or perform any other distracting activity. For at least 3 days during the run-in period, women will also complete daily voiding diaries, which will be used to further assess women's compliance and to collect data on baseline severity of overactive bladder symptoms. Women will also be asked to wear a wrist actigraph while they complete their voiding diaries, push a button on the actigraph to indicate when they go to bed and when they get up each night, and complete a simple sleep diary over this same 3-day period.

D.6.4 Baseline/Randomization Visit

A baseline visit will be scheduled one to two weeks after the screening visit and completion of the run-in procedures. Participants will return with their completed voiding diary, the demo RESPeRATE run-in device, and the wrist actigraph and sleep diary. Diary data will be abstracted, and data from the run-in device and the actigraph will be downloaded. Those who are non-adherent to RESPeRATE practice or the diary will not be eligible to continue. Blood pressure, heart rate, and respiratory rate will be re-measured; participants who have a blood pressure <100/60 will also be ineligible to continue. If the demo RESPeRATE device indicates

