home practice for at least 12 minutes on each of at least 6 days, the voiding diary is completed correctly on at least 3 days, and the diary reveals an average of at least 3 voiding or incontinence episodes per day associated with at least moderate urgency, and the participant meets other eligibility criteria and agrees to enroll in the study, she will be eligible for randomization to a regular active or control RESPeRATE device. Immediately following proof of eligibility, the study coordinator will randomize the participant, using the next sequential randomization envelope.

Following randomization, instruction in use of the active or control RESPeRATE device will be reviewed, and the participant will be asked to use the device for at least 15 minutes per day at home. The participant will be given the study phone number and instructed to call study staff for any questions or problems with the devices. Participants will be given a pamphlet providing brief information about usual care behavioral self-management of overactive bladder symptoms. Participants will be reminded not to take any medications known to affect overactive bladder symptoms during the treatment period.

Participants will also undergo non-invasive measurement of resting heart rate variability and pre-ejection period using the BIOPAC MP150 monitoring device at this visit (if they are randomized). They will complete questionnaires assessing condition-specific quality of life and anxiety and perceived stress symptoms.

D.6.5 Follow-up Visit (1 week)

After one week of treatment, participants will return to the clinic for early follow-up, bringing their RESPeRATE active or control devices. Downloaded RESPeRATE device data will be securely transferred to the study database. The study coordinator will review adherence with use of the active or control device, assess for side effects of treatment, and answer any questions. For safety monitoring, blood pressure, heart rate, and respiratory rate will be reassessed by study staff. Adverse events will be recorded on standardized forms. Each participant will also be given a new, blank voiding diary to complete for 3 days before her 6-week visit.

D.6.6 Follow-up Visit (6 weeks)

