After 6 weeks of treatment, women will return to the clinic for follow-up for assessment of adherence, side effects, and concurrent medications, and to address any questions. They will return their 2nd completed voiding diary, in which they will have recorded all voiding and incontinence episodes over a 3-day period and indicated whether these episodes were associated with no, mild, moderate, or severe urgency. Data from RESPeRATE devices will be downloaded before the device is returned to the participant. Blood pressure, heart rate, and respiratory rate will be measured by study staff. Adverse events will be recorded on standardized forms. Participants will complete the same self-administered questionnaires about condition-specific quality of life and anxiety and stress given at baseline visit.

D.6.7 Follow-up Phone Call (9 weeks)

After 9 weeks of treatment, the study coordinator will contact participants by telephone to review adherence with use of the RESPeRATE device, assess for side effects, and answer any questions. At the participant's request, or if there is a safety concern, this visit may also be conducted in person. Participants will be reminded that to start completing their next voiding diary at least 3 days before their 12-week visit, and to wear

the wrist actigraph and complete their sleep diary during this same 3-day period. They will be reminded to bring their completed voiding diary, their RESPeRATE device, and their actigraph and sleep diary with them to that 12-week visit.

D.6.8 12-Week Visit

The final clinic visit will take place approximately 12 weeks after screening or at the time a participant decides to discontinue participation in the trial. Participants will return their third completed voiding diary, the RESPeRATE device, and the wrist actigraph and sleep diary. Participants will complete the same self-administered questionnaires that were given at the baseline and 6-week visits. They will also complete a close-out questionnaire about their satisfaction with the study interventions and procedures. Physical exam measures of blood pressure, heart rate, and respiratory rate will be repeated. Participants will also undergo repeat assessment of heart rate variability and impedance cardiography. Participants will receive instructions and materials for completing and returning the 24-week mail-in voiding diary and questionnaire packet.

D.6.9 24-Week Mail-In

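### D.6.8 counts the final visit from screening, but the 12 weeks of assigned device use and the primary endpoint both start at the baseline/randomization visit

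*Combined protocol and SAP*

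**What the plan says.** On the final visit, D.6.8 reads: "The final clinic visit will take place approximately 12 weeks after screening or at the time a participant decides to discontinue participation". The same section has participants hand back the device and their third diary at that visit, so it ends assigned treatment and supplies the primary-outcome data.

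Other sections count from a later point:

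- **Start of assigned use.** D.4.2: "Participants who are randomized to the active intervention group will receive an active RESPeRATE device at the baseline visit". D.6.4 places randomization, and instruction in the assigned device, at this visit for both arms.
- **Gap between screening and baseline.** D.6.4: "A baseline visit will be scheduled one to two weeks after the screening visit and completion of the run-in procedures". D.6.3 puts a 7-day run-in between the two visits, on a demo device that does not pace breathing.
- **Length of assigned use.** D.4.1: "Participants in both groups will be instructed to use their devices for at least 15 minutes per day for 12 weeks". D.4.2 repeats this for the active arm: "Participants will be instructed to use RESPeRATE for at least 15 minutes per day for a total of 12 weeks". D.6.10 totals the home practice as 21 hours.
- **Interim contacts.** D.6.5: "After one week of treatment, participants will return to the clinic for early follow-up". D.6.6: "After 6 weeks of treatment, women will return to the clinic for follow-up". The 9-week call in D.6.7 is also counted in weeks of treatment.
- **Endpoint.** D.10.1 defines the primary outcome as change from baseline to 12 weeks, and the anxiety outcomes use the same interval.

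The opening paragraph of D.6 lists five in-person visits, Screening among them, and says that these and the calls fall within a 12-week period.

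**The concern.** D.6.8 is a scheduling rule that site staff would apply, and it governs the visit that supplies the primary outcome. It names screening as the starting point, while the visits before it are counted from the start of treatment. Because the run-in always precedes randomization, a visit 12 weeks after screening cannot follow 12 weeks on the assigned device for any participant. At stake are the length of treatment before the primary assessment and agreement between the visit schedule and the endpoint definition. Visits take place at two locations and the protocol gives no visit windows, so coordinators could count from different origins.

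**Working it through.** **Inputs.** Daily practice 15 minutes = 0.25 h and 12 weeks of use (D.4.1, D.4.2); total practice 21 h (D.6.10); final visit 12 weeks = 84 days after screening (D.6.8, read literally); baseline one to two weeks after screening and the run-in (D.6.4); run-in 7 days (D.6.3).

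**Step 1: the plan's own figure.** 12 weeks × 7 days × 0.25 h = 21 h. This matches D.6.10 exactly, so the stated total needs 12 full weeks on the assigned device.

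**Step 2: assigned use under D.6.8 as written.** Days on device = 84 − gap from screening to baseline. The D.6.4 sentence can be read in two ways.

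*Reading A: the one to two weeks run from screening (gap 7 to 14 days).*
- Gap 7: 84 − 7 = 77 days = 11 weeks; 77 × 0.25 = 19.25 h; 19.25/21 = 92% of plan.
- Gap 14: 84 − 14 = 70 days = 10 weeks; 70 × 0.25 = 17.5 h; 17.5/21 = 83% of plan.

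*Reading B: the one to two weeks run from the end of the run-in, which is assumed to start at screening (gap 7 + 7 = 14 to 7 + 14 = 21 days).*
- Gap 14: 10 weeks and 17.5 h, as above.
- Gap 21: 84 − 21 = 63 days = 9 weeks; 63 × 0.25 = 15.75 h; 15.75/21 = 75% of plan.

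**Step 3: fit with the neighbouring contacts.** With the origin at baseline, the final visit comes 12 − 9 = 3 weeks after the 9-week call. Under D.6.8 as written it comes 11 − 9 = 2 or 10 − 9 = 1 week after the call (reading A). At the far end of reading B, 9 − 9 = 0, so the visit and the call coincide.

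**Step 4: knock-on intervals under reading A.** The segment after week 6 used in D.10.4 would last 11 − 6 = 5 or 10 − 6 = 4 weeks instead of 6. The mail-in, set 12 weeks after device return (D.6.9), would fall 11 + 12 = 23 or 10 + 12 = 22 weeks after randomization instead of 24.

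**Step 5: could the run-in count towards the 12 weeks?** No. The demo device does not pace breathing, every participant uses it before assignment, and D.6.5 starts the count of treatment weeks after the baseline visit.

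**The case against.** The strongest reply is that the protocol already resolves this. The section is headed as the 12-week visit, the contacts before it count weeks of treatment, Appendix A numbers visits only after baseline, and D.10.1 ties the endpoint to baseline. D.6.8 also says *approximately*. A coordinator working from the whole schedule is unlikely to cut treatment short. Most of this stands: the intended origin can be inferred, which is why the point is minor. The qualifier does not remove the conflict, though. It allows scatter around a target, whereas here the target itself is at least a week early for every participant.

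A reader might infer that treatment will actually be shortened, that the primary comparison is biased, or that the study loses power. The documents do not support this. Nothing shows that visits will be booked from screening. The origin would shift equally in both arms. The calculation in D.10.2 uses a baseline mean, a control reduction, an SD, a correlation and a dropout rate, none of which depends on this phrase.

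A reader might also take the D.6 overview as evidence that screening is the true origin. It is better read as the same slip made twice, because the treatment-duration, interim-visit and endpoint text all contradict it.

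**Conclusion.** Wrong as written, low severity. D.6.8 conflicts with the 12 weeks of assigned use, with the visits counted in weeks of treatment, and with the baseline-to-12-week endpoint. Only if it were applied literally would assigned use fall to about 10 to 11 weeks (17.5 to 19.25 h of 21 h), or to 9 to 10 weeks (15.75 to 17.5 h) under the other reading of D.6.4. These figures assume practice at the minimum 15 minutes a day and a final visit exactly 84 days after screening; reading B also assumes that the run-in starts at screening. There is no between-arm bias and no effect on the sample size or analysis model. This is a drafting error in the visit schedule; the design is sound on this point.

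**What to change.** 1. In D.6.8, make the final visit due approximately 12 weeks after the baseline/randomization visit instead of after screening.
2. In the opening paragraph of D.6, state that the 12-week period runs from baseline and that screening and the run-in come before it.

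The cost is two wording changes. No visits, participants or analyses are added, and D.10.1 needs no edit because it already counts from baseline.

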To address this possibility, we propose to conduct a randomized trial of a mindfulness-based slow-breathing technique that has previously been shown to decrease anxiety and improve autonomic control. Women with OAB will practice slow-breathing exercises at home using a commercially-available guided-breathing device that requires limited individual instruction, is relatively inexpensive, and is FDA-approved for treatment of hypertension—another chronic condition associated with both autonomic dysfunction and anxiety. To enable rigorous evaluation of efficacy, women will be randomized to: 1) use a standard guided-breathing device to practice slowing their respiratory rate to 5 to 10 breaths per minute (BPM) for a minimum of 15 minutes per day (consistent with recommended use of the device to treat hypertension), or 2) use a visually-identical control device reprogrammed to promote breathing at a normal resting rate of 14 BPM. All women will also receive a pamphlet with information about behavioral self-management of OAB, consistent with usual care.

The proposed work is significant because it will provide new evidence to evaluate the efficacy and tolerability of a behavioral slow-breathing exercise program to treat OAB, and also evaluate autonomic dysfunction and anxiety symptoms as potential mediators of treatment effects. If successful, this research may help decrease the burden of one of the most common chronic health problems in women, as well as reduce morbidity and costs associated with anticholinergic OAB therapy.

D. RESEARCH DESIGN AND METHODS

D.1 General Study Design

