Because of the behavioral nature of the treatment interventions, study participants cannot be fully blinded to treatment assignment. However, several steps will be taken to minimize possible bias arising from lack of blinding. Participants will be told that they are participating in a study of two different types of relaxation therapy, slow-paced respiration versus music-listening, for treatment of overactive bladder symptoms. They will be told that the investigators do not yet know whether one form of therapy is more effective than the other.

in controlling bladder symptoms (which is true). All participant materials will be developed to avoid giving participants the impression that slow-paced respiration is believed to be more effective than relaxing music-listening in controlling overactive bladder. Information listed on clinicaltrials.gov and other public registries will also avoid implying that one form of therapy is more effective than the other.

When interacting with participants, study staff will refer to the RESPeRATE device as the “CURE study relaxation device” rather than a “RESPeRATE device,” since the control device will be used differently from a standard, commercially-available RESPeRATE device. Participant-oriented study materials will also refer to the device as a “relaxation device” and avoid referring to either RESPeRATE or Intercure Ltd.

The primary outcome, change in frequency of voiding or incontinence episodes associated with at least moderate urgency, will be assessed using 3-day voiding diaries, which are likely to be more resistant to bias than other types of self-report measures. Although clinical staff responsible for conducting study visits will not be blinded to treatment assignment (so that they can assist participants with problems using their RESPeRATE devices), the study investigators will be blinded to treatment assignment. A subset of voiding diaries from both the [name] and [name] sites will be reviewed by a blinded analyst for quality control.

D.4.6 Overactive bladder self-management pamphlet

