Because the main potential adverse effect of RESPeRATE is a decrease in blood pressure to symptomatic levels, resting blood pressure will be measured twice in the dominant arm at each study visit, and treatment with RESPeRATE will be discontinued in women with average blood pressure <90/50, and in those with blood pressure <100/60 as well as symptoms suggestive of hypotension such as dizziness. If a participant experiences dizziness while using RESPeRATE, she will also be asked to come to the clinic and practice using RESPeRATE under supervision, with blood pressure measured at the beginning and end of practice. In

published trials of RESPeRATE including a total of 492 participants,⁵⁶⁻⁶³ blood pressure lowering was contingent on higher blood pressure at baseline, such that use of the device in participants with systolic blood pressure <120 mmHg at baseline had no effect on blood pressure; no symptomatic hypotension was reported.

Other unexpected side effects will be assessed using standardized adverse event or serious adverse event forms. At each phone and in-person contact, participants will also be asked about any negative changes in their health. An adverse event will be defined as any undesirable sign, symptom, or medical condition that occurs after starting therapy, whether considered related to the study intervention or not. According to standard practice, adverse events will be classified as mild, moderate, or severe. Events that result in death or disability, are life threatening, or cause hospitalization or prolongation of hospitalization will be classified as serious adverse events and recorded on severe adverse event forms that also note the potential relationship to study interventions and any medical treatment or therapy provided in response to the event.

D.6 Study Visits and Procedures

This clinical trial involves 5 in-person study visits (Screening, Baseline, 1-Week, 6-Week, and 12-Week) and 2 telephone visits (3-Week and 9-Week) over a 12-week period. Additionally, women will complete daily RESPeRATE practice sessions at home, and will complete voiding diaries at home at 3 timepoints over this 12-week period. There is also a 24-week mail-in assessment, in which women will complete an additional voiding diary and packet of questionnaires and return them to study staff by mail.

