Staff will be trained to be courteous and discrete when administering questionnaires, obtaining physical exam measurements, and assessing heart rate variability and impedance cardiography, and to follow-up with referrals to appropriate medical personnel when measurements are outside allowable ranges. Participants will be told that they can ask to pause or discontinue measurements if they become uncomfortable.

Participants who report an allergy or sensitivity to adhesives can decline to undergo heart rate variability or impedance cardiography measurements. Study staff will be trained to remove the EKG electrodes and tape in ways that minimize skin irritation or reaction. Participants with an allergy to metal can wear the wrist actigraph monitor over their sleeve or use a wrist sports sweat band to protect their skin. They can also decline to undergo wrist actigraphy measurements as a non-essential study procedure.

D.8.3 Adverse event monitoring

At each phone and in-person contact, participants will also be asked about any negative changes in their health, which will be recorded as adverse events or serious adverse events on standardized forms. An adverse event will be defined as any undesirable sign, symptom, or medical condition that occurs after starting therapy, whether considered related to the study intervention or not. Medical conditions or diseases present before starting the intervention will only be considered adverse events if they worsen after starting the therapy. According to standard practice, adverse events will be classified as mild, moderate, or severe. Adverse event forms will also record whether the event resolved or continues.

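### Harms are elicited by an open question and unworded checks from staff who know the arm; reading one short symptom list to both arms would be a cheap improvement

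*Combined protocol and SAP*

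**What the plan says.** The general method is in D.8.3, and D.5.7 repeats it in nearly the same terms: "At each phone and in-person contact, participants will also be asked about any negative changes in their health, which will be recorded". The answers go onto standardized forms, with separate ones for serious events. No symptom is named in that question.

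The visit descriptions add a little. At week 1 the coordinator is to "assess for side effects of treatment, and answer any questions". Week 6 is a "follow-up for assessment of adherence, side effects, and concurrent medications". The week 9 call has a similar check. None gives wording or a list. D.6 schedules a week 3 call but has no subsection for it, and D.6.8 (week 12) mentions no side-effects check. Appendix A nevertheless marks an adverse events assessment at baseline and at weeks 1, 3, 6, 9 and 12.

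On who asks, D.4.5 says that "clinical staff responsible for conducting study visits will not be blinded to treatment assignment". On what is expected, D.5.7 says that "the main potential adverse effect of RESPeRATE is a decrease in blood pressure to symptomatic levels". Under D.5.7, D.7.4 and D.8.2 the intervention stops if average pressure is below 90/50, or if it is below 100/60 and the woman has symptoms of hypotension. D.5.7 adds: "If a participant experiences dizziness while using RESPeRATE, she will also be asked to come to the clinic" for supervised practice. Section C says that the trial will "provide new evidence to evaluate the efficacy and tolerability of a behavioral slow-breathing exercise program".

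**The concern.** An open question collects what a participant happens to think worth mentioning, and follow-up probing is left to the person asking. Here that person knows the arm. The protocol also gives staff reasons to expect different things in the two arms: D.5.7 names symptomatic hypotension for the device, while D.8.1 calls the device's risk minimal and says that controls may find the music irritating. Ascertainment of subjective complaints could therefore drift apart, in either direction.

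Two uses of the data are exposed. One is the descriptive tolerability comparison, together with the Data and Safety Monitor's reading of adverse effects on unblinded data (D.8.4). The other is the part of the safety procedure that turns on symptoms: women measured between 90/50 and 100/60, and women who become dizzy between clinic visits.

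**Working it through.** The plan gives no figure for this point, so the check sets the sections side by side.

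**Step 1. What happens at each contact after randomisation (D.6, D.8.3, Appendix A).**

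| Contact | Open question | Side-effects check described in D.6 | Blood pressure scheduled |
|---|---|---|---|
| Week 1, clinic | yes | yes, no wording | yes |
| Week 3, phone | yes | no subsection | no |
| Week 6, clinic | yes | yes, no wording | yes |
| Week 9, phone | yes | yes, no wording | no, unless held in person |
| Week 12, clinic | yes | none described | yes |

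That makes 5 contacts, 3 with a scheduled reading and 5 − 3 = 2 without. The gaps between readings are 6 − 1 = 5 weeks and 12 − 6 = 6 weeks, each with one phone contact.

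**Step 2. Who asks.** Visit staff are unblinded (D.4.5). The study coordinator opens the randomisation envelope (D.6.4) and makes the week 1 and week 9 checks (D.6.5, D.6.7). At least those two checks are made by a role that knows the arm.

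**Step 3. Where symptoms are named.** Dizziness is named in D.5.7 and D.7.4; D.8.2 adds fatigue and orthostatic symptoms. In each place the symptom is either a reason for the woman to come in or a condition of the stopping rule. Nowhere is it an item put to her at a scheduled contact.

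**Step 4. What the stopping rule needs.** The limb below 90/50 needs only a reading. The limb below 100/60 needs a reading and symptoms. Staff who record such a reading must establish symptoms to apply the rule, but the documents do not say how, and by then they know both the reading and the arm. D.7.4 refers to the study interventions, so the rule covers both arms. Readings are seated and resting (D.5.6), so they do not by themselves show the orthostatic symptoms that D.8.2 has in mind.

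**Step 5. Which analyses depend on it.** D.10 contains no between-arm harms analysis. The primary outcome comes from voiding diaries. What is exposed is description and monitoring, not a planned test.

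**Step 6. Size.** A number would need the frequency of mild complaints and the chance of eliciting one in each arm. The documents give neither. If both arms are asked alike, the manner of asking adds no difference.

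**The case against.** The case against is substantial.

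- **Both arms get the same stated question.** Nothing in the documents shows staff asking differently by arm. This stands: the point is a better method of elicitation, not a demonstrated bias.
- **The forms are not shown.** D.5.7 says that side effects are assessed on standardized forms, and D.9.1 says that most forms exist from earlier studies. A list may already be there. This stands, and confirming it would settle most of the point.
- **Symptoms have their own route.** D.8.2 tells women to come in if they develop dizziness, fatigue or orthostatic symptoms, without waiting to be asked. D.6.7 allows week 9 in person at the participant's request or for a safety concern. A reader might infer that a complaint drawn out on the phone is the only way to an extra reading at weeks 3 and 9. The documents do not support that.
- **The expected risk is low.** Women below 100/60 are excluded at screening and again at baseline. D.5.7 reports no symptomatic hypotension in published trials with 492 participants, and no pressure effect in those starting below 120 mmHg systolic. This limits how many women the symptom limb is likely to concern.
- **Harms are not one of the three aims.** True, but Section C does promise evidence on tolerability, and the monitor reviews adverse effects.
- **A list covering only hypotension would miss control-arm complaints, and asking about fatigue could generate visits.** Both are fair, and the fix allows for them.

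What remains is that relying on a woman to recognise a symptom and act on it is weaker than also asking her about it, in the same words in both arms, at a contact that takes place anyway.

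**Conclusion.** The point holds as a minor, inexpensive improvement. As documented, harms are elicited by an open question and unworded checks from staff who know the arm, and the symptom limb of the stopping rule uses symptoms that no scheduled contact is said to ask about by name.

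A reader might go further and infer that the recorded harms will be biased for or against slow breathing, or that women who should stop will be missed. The documents support neither. They show an opportunity for uneven asking, not its occurrence, and they give no basis for a direction or a size. The limb below 90/50 does not depend on symptoms, and the limb below 100/60 can still be applied by asking once a low reading is seen. Nor does the point touch efficacy.

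The conclusion assumes that the forms do not already contain a symptom list read to both arms. If they do, stating so in D.8.3 is enough.

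**What to change.** In D.8.3, specify one short fixed list, read in the same words to both arms: dizziness, fatigue, other orthostatic symptoms, and one item on discomfort or irritation from the device or its music.

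- **When:** once at the baseline visit before randomisation, then at weeks 1, 3, 6, 9 and 12. Appendix A already marks an adverse events assessment at all six. The baseline reading is taken before anyone knows the arm, and it makes D.8.3's rule workable that pre-existing conditions count only if they worsen.
- **Order:** before the open question and, at clinic visits, before blood pressure is taken.
- **Recording:** flag each event as solicited or spontaneous.
- **Action:** a solicited symptom triggers an extra clinic blood pressure check only if it is new or worse than at baseline. The pressure thresholds and the instruction to women to come in on their own initiative stay as set.

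The cost is one scripted form and one source field. If a reading takes 1 to 3 minutes (an assumption), 160 women × 6 readings = 960 readings, or 960 ÷ 60 = 16 to 960 × 3 ÷ 60 = 48 staff hours over the trial. More minor complaints will be recorded in both arms, and a few extra blood pressure visits are possible. The list adds no scheduled readings, so the 5- and 6-week gaps remain. It reduces, but does not remove, bias from unblinded staff and participants.
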